## **12.7 Secondary Analysis**

The analysis of PD at 3 months, CAL at 3 and 6 months will be also performed, as a secondary endpoint.

There will be an adjustment for multiplicity for the secondary testing of CAL and PD within the As Exposed Set as defined in section 12.1.5.

Urinary NEQ, total NNAL and CEMA levels (concentration data adjusted for creatinine will be analyzed on a logarithmic scale) using an MMRM with the BoExp geometric mean value as the dependent variable, adjusting for daily cigarette consumption at baseline and sex, visit, baseline BoExp level, exposure group and its interaction with visit. Site will be included as a random effect. The modeling assumptions will be evaluated similar to that in the primary analysis.

Descriptive statistics for the BoExp will be summarized at each visit by exposure group and overall (across all patients). The primary endpoint will also be summarized by strata (daily cigarette consumption and sex).

The other secondary endpoints will be summarized descriptively at each visit by exposure group and overall (across all patients) in the As Exposed Set (unless otherwise defined):

- Change in mean full-mouth PD.
- Change in mean full-mouth CAL.
- Mean PD change in sites with initial PD < 4 mm, and with initial PD of 4 mm to < 5mm, 5 mm to < 6 mm, 6 mm to < 7 mm and  $\geq$  7 mm.

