### **Confidentiality Statement**

---

Data and information contained in this document are considered to constitute trade secrets and confidential commercial information, and the legal protections provided to such trade secrets and confidential information are hereby claimed under the applicable provisions of applicable law. No part of this document may be publicly disclosed without the written consent of Philip Morris Products S.A.

---

- Mean CAL change in sites with initial PD < 4 mm, and with initial PD of 4 mm to < 5mm, 5 mm to < 6 mm, 6 mm to < 7 mm and  $\geq 7$  mm.
- Change in the number of sites with PD < 4 mm, with PD 4 mm to < 5mm, with PD 5 mm to < 6 mm , with PD 6 mm to < 7 mm and with PD  $\geq 7$  mm. The number of sites will be treated as a continuous variable.
- Change in BOP scores, GI score, tooth mobility (grade) and PCR.
- Number of tobacco or nicotine containing products used, (including cigarettes and *HeatSticks*) based on self-reporting.
- Incidence of AEs/SAEs and device events will be presented as frequencies and percentages of the number of patients per group in the Safety Set.

Additionally, the analyses will be performed on the FAS; PP and Adherent Use populations as a supportive sensitivity analysis. Any sub group analyses will be defined in the SAP.

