3.2 Secondary Objectives and Endpoints

The secondary objectives of this study are:

1. To evaluate the effect of switching to IQOS use compared to continued cigarette smoking on the response of PD and clinical attachment level (CAL) to mechanical periodontal therapy over time.

Endpoints (3 and 6 months):

- Mean PD change in sites with initial PD ≥ 4 mm after mechanical periodontal therapy (3 month only).
- Mean CAL change in sites with initial PD ≥ 4 mm after mechanical periodontal therapy (3 and 6 months).

2. To evaluate the differences of periodontal parameters in the response to periodontal therapy in patients who switch to IQOS use compared to those who continue to smoke cigarettes.

Endpoints (3 and 6 months):

- Change in mean full-mouth CAL
- Change in mean full-mouth PD
- Mean PD change in sites with initial PD < 4 mm, and with initial PD of 4 mm to < 5 mm, 5 mm to < 6 mm, 6 mm to < 7 mm and ≥ 7 mm
- Mean CAL change in sites with initial PD < 4 mm, and with initial PD of 4 mm to < 5 mm, 5 mm to < 6 mm, 6 mm to < 7 mm and ≥ 7 mm
- Change in the number of sites with PD < 4 mm, with PD 4 mm to < 5 mm, with PD 5 mm to < 6 mm, with PD 6 mm to < 7 mm and with PD ≥ 7 mm
- Change in gingival index (GI) score
- Change in tooth mobility (grade)

Confidentiality Statement

Data and information contained in this document are considered to constitute trade secrets and confidential commercial information, and the legal protections provided to such trade secrets and confidential information are hereby claimed under the provisions of applicable law. No part of this document may be publicly disclosed without the written consent of Philip Morris Products S.A

- Change in plaque control record (PCR)
 - Change in bleeding on probing (BOP) scores
3. To evaluate the levels of biomarkers of exposure (BoExp) over the exposure period in patients who switch to IQOS use and patients who continue to smoke cigarettes.

Endpoint (3 and 6 months):

- Urinary nicotine equivalents (NEQ), total 4-[methylnitrosamino]-1-[3-pyridyl]-1-butanol (NNAL) and 2-cyanoethylmercapturic acid (CEMA).
4. To describe self-reported tobacco or nicotine containing product use over the duration of the study in patients switching to IQOS use and patients who continue to smoke cigarettes.

Endpoint:

- Number of self-reported tobacco or nicotine containing product use
5. To monitor safety.

Endpoint:

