7 CHANGES FROM THE PROTOCOL SPECIFIED STATISTICAL ANALYSES

Changes to “As Exposed Set” to exclude patients with major protocol deviations that affect evaluability of the data. The removal of the “Adherent Use Set” from the analysis sets.

Confidentiality Statement

Data and information contained in this document are considered to constitute trade secrets and confidential commercial information, and the legal protections provided to such trade secrets and confidential information are hereby claimed under the provisions of applicable law. No part of this document may be publicly disclosed without the written consent of Philip Morris Products S.A.

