Analysis variables	: 
 • Teeth Count • Pocket Depth (mm) • Clinical Attachment Loss (mm) • Bleeding on Probing (%) • Gingival Index • Plaque Control Record (%)
Output	15.2.2.7 Baseline Characteristics of Periodontal Disease - As Exposed Set -

Summary Table of Medical History	
Population	: 
 • Safety Sets 
 ➤ Product use pattern
Contents	: The number and percentage of patients experiencing medical history and the number of medical history will be counted by Medical Dictionary for Regulatory Activities (MedDRA, Version 20.0 or higher) System Organ Class (SOC) term and Preferred Term (PT). All cases collected on the form for medical history of CRF (MHCAT="MEDICAL HISTORY") will be tabulated.
Definition	: Medical history is defined as any condition that started and ended prior to ICF signature.
Remark	: SOC and PT will be sorted by alphabetical order.
Output	15.2.3.1 Summary Table of Medical History - Safety Set - 15.3.3.1 Listing of Medical History/ Concomitant disease and Periodontal Disease - Safety Set -

Summary Table of Periodontal Disease History

Confidentiality Statement

Data and information contained in this document are considered to constitute trade secrets and confidential commercial information, and the legal protections provided to such trade secrets and confidential information are hereby claimed under the provisions of applicable law. No part of this document may be publicly disclosed without the written consent of Philip Morris Products S.A

Summary Table of Periodontal Disease History	
Population	: 
 • Safety Sets 
 ➤ Product use pattern
Contents	: The number and percentage of patients experiencing periodontal disease and the number of periodontal disease history will be counted by Medical Dictionary for Regulatory Activities (MedDRA, Version 20.0 or higher) SOC and PT. All cases collected on the form for periodontal disease history (MHCAT=" PERIODONTAL DISEASE HISTORY") will be tabulated.
Definition	: Periodontal disease history is defined as any condition that started and ended prior to ICF signature.
Remark	: SOC and PT will be sorted by alphabetical order.
Output	15.2.3.3 Summary Table of Periodontal Disease History - Safety Set -

Summary Table of Concomitant Disease	

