9.5.1.2 Supportive Analysis for Primary Objective

Supportive/Sensitivity Analyses of Change from Baseline in PD	
Population	: 
 Full Analysis Set Per Protocol Set
Contents	: Refer to " Primary Analysis "
Target visit	: 
 V3 (3 months) V4 (6 months)

Confidentiality Statement

Data and information contained in this document are considered to constitute trade secrets and confidential commercial information, and the legal protections provided to such trade secrets and confidential information are hereby claimed under the provisions of applicable law. No part of this document may be publicly disclosed without the written consent of Philip Morris Products S.A

Supportive/Sensitivity Analyses of Change from Baseline in PD	
Sample code	Refer to " Primary Analysis "
Output	
15.4.6.1 Analysis of Change from Baseline in Pocket Depth (mm) with Initial Pocket Depth \geq 4 mm - Full Analysis Set, Per Protocol Set -
 
15.4.6.2 Regression Coefficients and Graphical Diagnostics of Analysis of Change from Baseline in Pocket Depth (mm) - Full Analysis Set , Per Protocol Set -

Summary Table of Mean Full-Mouth PD by (i) Daily Cigarette Consumption, (ii) Disease Severity (iii) Age group	
Population	: 
 As Exposed Set Full Analysis Set Per Protocol Set
Contents	: Refer to Descriptive statistics
Analysis variables	: 
 Mean full-mouth PD Change of mean full-mouth PD
Target visit	
 Baseline V3 (3 months) V4 (6 months)
Remarks	Output titles to be changed depending on target population.
Output	
15.2.6.1 Summary Table of Mean Full-Mouth Pocket Depth (mm) by Disease Severity - As Exposed Set, Full Analysis Set, Per Protocol Set -
 
15.2.6.2 Summary Table of Mean Full-Mouth Pocket Depth (mm) by Daily Cigarette Consumption - As Exposed Set, Full Analysis Set, Per Protocol Set -
 
15.2.6.3 Summary Table of Mean Full-Mouth Pocket Depth (mm) by Sex - As Exposed Se, Full Analysis Set, Per Protocol Set -
 
15.2.6.4 Summary Table of Mean Full-Mouth Pocket Depth (mm) by Age Group - As Exposed Set, Full Analysis Set, Per Protocol Set -

Confidentiality Statement

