Output	
15.1.7.5 Plot of Full-Mouth Clinical Attachment Level (mm) and 95% CI vs Visit by Product Use Categories - As Exposed Set -
 
15.1.7.6 Plot of Full-Mouth Clinical Attachment Level (mm) and 95% CI vs Visit by Product Use Categories and Disease Severity - As Exposed Set -
 
15.1.7.7 Plot of Full-Mouth Clinical Attachment Level (mm) and 95% CI vs Visit by Product Use Categories and Daily Cigarette Consumption - As Exposed Set -
 
15.1.7.8 Plot of Full-Mouth Clinical Attachment Level (mm) and 95% CI vs Visit by Product Use Categories, Disease Severity and daily Cigarette Consumption - As Exposed Set -
 
15.1.7.9 Plot of Full-Mouth Clinical Attachment Level (mm) and 95% CI vs Visit in Patients with Initial Pocket Depth ≥ 4 mm - As Exposed Set -
 
15.2.7.1 Descriptive Statistics of Mean Full-Mouth Clinical Attachment Level (mm) and 95% CI- As Exposed Set -
 
15.3.7.1 Listing for Clinical Attachment Level (mm) Value - As Exposed Set -
 
15.1.9.5 Plot of Clinical Attachment Loss (mm) for initials sites with Pocket Depth ≥ 4 mm - As Exposed Set -

Summary Table of Change in PD in Sites Based on Baseline PD Level	
Population	: • As Exposed Set
Contents	: Refer to Descriptive statistics In addition, a bar graph representing the mean PD in sites with different Initial PD, and a heatmap of PD against time by product use category will be created.
Analysis variables	: • PD • Change of mean PD

Confidentiality Statement

Data and information contained in this document are considered to constitute trade secrets and confidential commercial information, and the legal protections provided to such trade secrets and confidential information are hereby claimed under the provisions of applicable law. No part of this document may be publicly disclosed without the written consent of Philip Morris Products S.A

Summary Table of Change in PD in Sites Based on Baseline PD Level	
Category	Initial PD of 
 • PD < 4 mm • 4 mm ≤ PD < 5mm • 5 mm ≤ PD < 6 mm • 6 mm ≤ PD < 7 mm • PD ≥ 7 mm
Target visit	
 • Baseline • V3 (3 months) • V4 (6 months)
Output	15.2.7.2 Summary Table of Change in Pocket Depth (mm) in Sites based on Initial Pocket Depth (mm) Level - As Exposed Set - 15.1.7.14 Mean Pocket Depth (mm) in Sites with Different Initial Pocket Depth (mm) - As Exposed Set - 15.1.9.3 Heatmap of Pocket Depth (mm) Level Count by Time and Product Use Categories - As Exposed Set -

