Data and information contained in this document are considered to constitute trade secrets and confidential commercial information, and the legal protections provided to such trade secrets and confidential information are hereby claimed under the provisions of applicable law. No part of this document may be publicly disclosed without the written consent of Philip Morris Products S.A

Summary Table of Periodontal Examination (BOP, GI, Tooth mobility and PCR)	
Population	: 
 • As Exposed Set 
 ➤ Product use pattern categories
Contents	: Refer to Descriptive statistics For GI and Tooth Mobility, in addition to the descriptive statistics shift tables will be constructed based on the individual (discrete) values. Scatter plots of GI and Tooth Mobility vs Visit by Product Use, Initial PD level will be plotted as well.
Analysis variables	: 
 • BOP (%) • GI • Tooth Mobility • PCR (%)
Target visit	
 • Baseline • V3 (3 months) • V4 (6 months)
Output	
15.2.7.11 Descriptive Statistics of Periodontal Examination (Bleeding On Probing (%)) - As Exposed Set -
 
15.2.7.12 Descriptive Statistics of Periodontal Examination (Gingival Index) - As Exposed Set -
 
15.2.7.13 Descriptive Statistics of Periodontal Examination (Tooth Mobility) - As Exposed Set -
 
15.2.7.14 Descriptive Statistics of Periodontal Examination (Plaque Control Record (%)) - As Exposed Set -
 
15.2.7.15 Shift Table in Number of Each Category for Gingival Index - As Exposed Set -
 
15.2.7.16 Shift Table in Number of Each Category for Tooth Mobility - As Exposed Set -
 
15.3.7.3 Listing for Bleeding On Probing (%) Assessment - As Exposed Set -
 
15.3.7.4 Listing for Plaque Control Record (%) Assessment - As Exposed Set -
 
15.3.7.5 Listing for Gingival Index Assessment - As Exposed Set -
 
15.3.7.6 Listing for Calculated Bleeding On probing (%) and Plaque Control Record (%) - As Exposed Set -

Confidentiality Statement

Data and information contained in this document are considered to constitute trade secrets and confidential commercial information, and the legal protections provided to such trade secrets and confidential information are hereby claimed under the provisions of applicable law. No part of this document may be publicly disclosed without the written consent of Philip Morris Products S.A

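### Eight of the nine objective-2 periodontal endpoints are tabulated by product use only, with no summary by randomised arm, although Protocol 12.7 most naturally calls for FAS and PP versions

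*SAP*

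**What the plan says.** SAP 3.2 gives secondary objective 2 as: "To evaluate the differences of periodontal parameters in the response to periodontal therapy in patients who switch to IQOS use compared to those who", the comparator being patients who go on smoking. Nine periodontal endpoints follow.

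Protocol 12.7 first fixes the main presentation: "The other secondary endpoints will be summarized descriptively at each visit by exposure group and overall (across all patients) in the As Exposed Set". It lists the endpoints, including all nine periodontal ones, and directly after the list adds: "Additionally, the analyses will be performed on the FAS; PP and Adherent Use populations as a supportive sensitivity analysis".

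In SAP 9.5.2.1 the population row for these endpoints names one set. Examples are "15.2.7.2 Summary Table of Change in Pocket Depth (mm) in Sites based on Initial Pocket Depth (mm) Level - As Exposed Set" and "15.2.7.11 Descriptive Statistics of Periodontal Examination (Bleeding On Probing (%)) - As Exposed Set". Full-mouth pocket depth (PD) is the exception, through SAP 9.5.1.2: "15.2.6.1 Summary Table of Mean Full-Mouth Pocket Depth (mm) by Disease Severity - As Exposed Set, Full Analysis Set, Per Protocol Set", with sister tables by cigarette consumption, sex and age.

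SAP 9.1.3.1 sets the grouping: the As Exposed and Safety sets are summarised by product exposure, and all other sets by randomisation arm. SAP 8.2 and 8.3 confirm that the FAS and PP are analysed by randomised product.

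SAP section 7 declares two departures from the protocol. One changes the As Exposed Set "to exclude patients with major protocol deviations that affect evaluability of the data". The other removes the Adherent Use Set.

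**The concern.** Objective 2 asks whether periodontal response differs between patients who switch and patients who go on smoking. Protocol 4.1 expects several of these measures (gingival index, mobility, plaque, bleeding) to illustrate a benefit of switching for general oral health, so the tables are likely to be read comparatively even though they carry no test.

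Product-use groups are formed after randomisation from self-report. Patients who keep to an assigned product may also differ in oral hygiene, which would bear directly on plaque and bleeding. That is plausible, but the documents do not establish it. A by-arm table beside the product-use table lets a reader see whether the two agree. For eight endpoints that second view is missing, and the SAP does not say that it was dropped.

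**Working it through.** **1. Endpoints against outputs.** Each SAP 3.2 objective-2 endpoint was matched to its table in SAP 9.5.1 to 9.5.2.2 and to the list in SAP 13.1.1.

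| Endpoint | SAP table | Population |
|---|---|---|
| Full-mouth CAL | 15.2.7.1 | As Exposed |
| Full-mouth PD | 15.2.5.1 | As Exposed |
| Full-mouth PD, split | 15.2.6.1 to 15.2.6.4 | As Exposed, FAS, PP |
| PD change by initial PD | 15.2.7.2 | As Exposed |
| CAL change by initial PD | 15.2.7.3 | As Exposed |
| Number of sites by PD level | 15.2.7.4 | As Exposed |
| BOP | 15.2.7.11 | As Exposed |
| GI | 15.2.7.12, 15.2.7.15 | As Exposed |
| Tooth mobility | 15.2.7.13, 15.2.7.16 | As Exposed |
| PCR | 15.2.7.14 | As Exposed |

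Nine endpoints, one with any FAS or PP table: 9 − 1 = 8 without. The related figures and listings are also As Exposed only.

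**2. Does the supportive section fill the gap?** SAP 9.5.2.2 repeats on the FAS and PP the models for PD at 3 months, CAL at 3 and 6 months in sites with initial PD of at least 4 mm, and the biomarkers. The PD and CAL models belong to objective 1 and the biomarkers to objective 3. None is an objective-2 endpoint.

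**3. Possible size of selection in the product-use comparison.** The plan gives no figure for this, so what follows is an illustration. Inputs from the plan are 86 per arm (64/(1 − 0.25) = 85.3, rounded up, which reproduces Protocol 12.2) and 10% non-adherence (SAP section 6). Assumed: no true product effect, and non-adherers averaging d = 0.5 SD below their arm mean. The documents give no source for d.

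- Leavers per arm: 0.10 × 86 = 8.6. Their summed deficit is 8.6 × 0.5 = 4.3.
- Patients staying in the IQOS arm: +4.3/77.4 = +0.056 SD.

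| Where non-adherers go | IQOS users | Cigarette users | Difference |
|---|---|---|---|
| Equal crossover both ways | (4.3 − 4.3)/86 = 0 | (4.3 − 4.3)/86 = 0 | 0 |
| IQOS-arm leavers become dual users, none leave the cigarette arm | +0.056 | 0 | 0.056 SD |
| Only IQOS-arm leavers cross, to cigarettes | +0.056 | −4.3/94.6 = −0.045 | 0.10 SD |

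The by-arm difference is 0 in every row. The results are proportional to d: the last row becomes 0.04 SD at d = 0.2 and 0.20 SD at d = 1.0. The direction is assumed as well; if only cigarette-arm leavers crossed to IQOS, the sign would reverse.

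**The case against.** **The protocol sentence may mean the models only.** In Protocol 12.6 the parallel sentence follows the description of the mixed model and comes before the descriptive text. In 12.7 the endpoints are assigned to the As Exposed Set before the supportive sentence appears. The last item in that list is adverse-event incidence, which is assigned to the Safety Set, so the sentence cannot apply literally to every item. On the models-only reading, SAP 9.5.1.2 and 9.5.2.2 deliver what was asked and section 7 has nothing to declare. This reading is possible and cannot be excluded. Against it, the 12.7 sentence directly follows the periodontal list and carries no limit to models, and the SAP itself plans FAS and PP descriptive tables for full-mouth PD, though it files them under the primary objective. A reader might infer a plain breach of the protocol; the text supports only a likely, undeclared departure.

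**Changes can be reported elsewhere.** Protocol 12.1 and SAP section 1 send changes to the study report, and SAP section 1 lets table titles and numbering change without amendment. Neither explains why section 7 lists two changes and not this one, and a population row is neither a title nor a number.

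**Little hangs on it.** Grouping by product use is the prespecified main approach, and objective-2 endpoints have no hypothesis. The tested periodontal endpoints (PD and CAL at 3 and 6 months) all have planned FAS and PP models. For full-mouth PD, two of the four tables split by randomisation strata, so the overall arm mean follows by weighting with the reported counts. All of this stands. It limits the point to descriptive reporting.

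**Baseline is partly shown by arm.** A reader might infer from "15.2.2.7 Baseline Characteristics of Periodontal Disease - As Exposed Set" that periodontal balance between the arms cannot be checked at all. That is not so: table 15.2.2.4 gives the severity stratum by arm, and tables 15.2.6.1 to 15.2.6.4 include baseline full-mouth PD for the FAS and PP. Only tooth count, CAL, BOP, GI and PCR lack a by-arm baseline. Protocol 12.5, which governs baseline, promises by-arm summaries for demographic variables only.

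**Conclusion.** The point holds as one of descriptive reporting. The count of eight in nine is exact. That the protocol requires by-arm tables is the most natural reading of 12.7, not the only one.

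No test, error rate or sample size is affected, and nothing here bears on the primary result. The size of any bias is unknown. A reader might take 0.10 SD as its expected size, but that needs one-way crossover from the IQOS arm to cigarettes and an unsourced 0.5 SD deficit. Under the same non-adherence rate and deficit, equal crossover gives 0 and a move to dual use gives 0.056 SD. The illustration shows that a gap between the product-use and by-arm views can arise with no true effect. It does not show that one will.

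By-arm tables would be protected by randomisation only as far as the FAS is: SAP section 8 removes users of other products from every set except the Safety Set. The change is worth making because it costs almost nothing and gives eight endpoints a comparison they now lack.

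**What to change.** In SAP 9.5.2.1 or 9.5.2.2, add the FAS and PP, by randomisation arm, to the population rows of tables 15.2.7.1 to 15.2.7.4 and 15.2.7.11 to 15.2.7.16, and update SAP 13.1.1 to match. If the sponsor reads Protocol 12.7 as covering models only, state in SAP section 7 that the remaining objective-2 endpoints are reported by product use alone, and why.

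Optionally, and not required by the protocol, add the FAS to table 15.2.2.7 so that baseline tooth count, CAL, BOP, GI and PCR can be compared by arm.

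The cost is SAP and table-shell wording plus reruns of existing programs with a different set and column variable. No new data, patients or procedures are needed.

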9.5.2.2 Supportive Analysis for Secondary Objectives

Summary Table of Supportive/Sensitivity Analyses to Evaluate the Change from Baseline in PD at V3 / CAL at V3 and V4

Population	:	
 • Full Analysis Set • Per Protocol Set
Contents	:	
The model will include the either PD or CAL change from baseline as the dependent variable, adjusting for the following covariates;
 
 • The same model described in “Primary Analysis” will be used.
Target visit	:	
 • V3 (3 Months) for PD • V3 (3 Months)/ V4 (6 Months) for CAL
Remarks	:	
 • Statistical tests for PD at V3, CAL and V4 and V3 are performed in a sequential manner as detailed in section 9.1.8. • The same model for the primary analysis will be used with both V3 and V4 data included, PD at 3 months will be reported only if the test for PD between CC and IQOS at 6 months is significant. • If the test between Cigarette User and IQOS User categories for PD is significant at V3, then the model with change from baseline CAL will be fitted with both V3 and V4 data and the test between Cigarette User and IQOS User categories for CAL

Confidentiality Statement

Data and information contained in this document are considered to constitute trade secrets and confidential commercial information, and the legal protections provided to such trade secrets and confidential information are hereby claimed under the provisions of applicable law. No part of this document may be publicly disclosed without the written consent of Philip Morris Products S.A

Summary Table of Supportive/Sensitivity Analyses to Evaluate the Change from Baseline in PD at V3 / CAL at V3 and V4

	
at V4 will be reported.
 
 If the test between Cigarette User and IQOS User categories for CAL at V4 is significant, then the test between Cigarette User and IQOS User categories for CAL at V3 will be reported.
Sample code	Refer to " Primary Analysis "
Output	
15.4.8.1 Analyses of Change from Baseline in Clinical Attachment Level (mm) with Initial Pocket Depth \geq 4 mm - Full Analysis Set, Per Protocol Set -
 
15.4.8.2 Regression Coefficients and Graphical Diagnostics of Analysis of Change from Baseline in Clinical Attachment Level (mm) - Full Analysis Set, Per Protocol Set -

Summary Table of Supportive/Sensitivity Analyses for BoExp Geometric Mean Value

Population	: 
 Full Analysis Set Per Protocol Set
Contents	: Refer to "Summary Table of Analysis for BoExp Geometric mean value".
Sample code	Refer to " Primary Analysis "
Output	
15.4.8.3 Analysis of NEQ Adjusted for Creatinine (mg/g creat) (Biomarkers of Exposure) Geometric Mean Value -Full Analysis Set, Per Protocol Set -
 
15.4.8.4 Regression Coefficients and Graphical Diagnostics of Analysis of Change from Baseline in NEQ Adjusted for Creatinine (mg/g creat) (Biomarkers of Exposure) - Full Analysis Set, Per Protocol Set -
 
15.4.8.5 Analysis of Total NNAL Adjusted for Creatinine (pg/mL creat) (Biomarkers of Exposure) Geometric Mean Value - Full Analysis Set, Per Protocol Set -
 
15.4.8.6 Regression Coefficients and Graphical Diagnostics of

Confidentiality Statement

Data and information contained in this document are considered to constitute trade secrets and confidential commercial information, and the legal protections provided to such trade secrets and confidential information are hereby claimed under the provisions of applicable law. No part of this document may be publicly disclosed without the written consent of Philip Morris Products S.A

Summary Table of Supportive/Sensitivity Analyses for BoExp Geometric Mean Value

	
Analysis of Change from Baseline in Total NNAL Adjusted for Creatinine (pg/mL creat) (Biomarkers of Exposure) - Full Analysis Set, Per Protocol Set -
 
15.4.8.7 Analysis of CEMA Adjusted for Creatinine (ng/mL creat) (Biomarkers of Exposure) Geometric Mean Value - Full Analysis Set, Per Protocol Set -
 
15.4.8.8 Regression Coefficients and Graphical Diagnostics of Analysis of Change from Baseline in CEMA Adjusted for Creatinine (ng/mL creat) (Biomarkers of Exposure) - Full Analysis Set, Per Protocol Set -

--	--

Confidentiality Statement

Data and information contained in this document are considered to constitute trade secrets and confidential commercial information, and the legal protections provided to such trade secrets and confidential information are hereby claimed under the provisions of applicable law. No part of this document may be publicly disclosed without the written consent of Philip Morris Products S.A

